PROJECT TITLE:

Web-MAP for children with chronic pancreatitis (WebMAP- CP)

PRINCIPAL INVESTIGATOR:

Name: [name]
Department: Child Health, Behavior and Development
[contact]
Email Address: [contact]

Contents

1.	Objectives.....	4
2.	Background.....	4
3.	Study Endpoints	7
4.	Drugs, Devices and Biologics	7
5.	Procedures Involved	7
6.	Data and Specimen Banking	9
7.	Sharing of Results	10
8.	Study Timelines	10
9.	Study Population	10
10.	Number of Subjects	11
11.	Withdrawal of Subjects	11
12.	Risks to Subjects.....	12
13.	Potential Benefits to Subjects	13
14.	Data Analysis/Management	13
15.	Confidentiality	14
16.	Provisions to Monitor Data to Ensure the Safety of Subjects	15
17.	Use of Social Media	16
18.	Research Related Injury.....	16
19.	Recruitment Methods	16
20.	Consent/Assent Process	17
21.	Process to Document Consent in Writing	19
22.	HIPAA Authorization and RCW Criteria	20
23.	Payments/Costs to Subjects	21
24.	Setting.....	21
25.	Resources Available.....	21
26.	Coordinating Center Procedures	22
27.	Good Clinical Practice.....	22

1. Objectives

1.1. Purpose, specific aims, or objectives:

This project will deliver a first ever randomized, double-blinded and placebo controlled nonpharmacological pain intervention to children with CP/ARP and potentially identify patient-specific biological and psychosocial factors associated with favorable versus poor responsiveness to CBT to enable precision medicine approaches, consistent with priorities of the Federal Pain Research Strategy.

Aim 1. To determine the efficacy of web-based CBT in children with CP/ARP.

Aim 2. To identify the genetic co-variants associated with treatment response to web-based CBT.

Aim 3. To identify clinical and psychosocial factors associated with treatment benefit from web-based CBT.

1.2. Hypotheses to be tested:

Hypothesis 1: Children receiving CBT will have greater reductions in pain-related disability (primary outcome), pain, anxiety and depressive symptoms, opioid use, and HRQOL (secondary outcomes) compared to the education control group. To test this hypothesis, we will conduct a randomized and double-blinded controlled trial of web-based CBT (WebMAP) vs education (WebED). We will evaluate changes in pain, HRQOL, emotional functioning, medication use, health care utilization at baseline, 2 months, and 6 months.

Hypothesis 2: Genetic co-variants associated with pancreatitis, inflammation, lipid and drug metabolism will predict response to therapy. To test this hypothesis, we will evaluate targeted next generation sequencing of genes involved in pancreatitis risk (CASR, CFTR, CTSC, SBD5, SBDSP – pseudogene, SPINK1, CEL, CELP – pseudogene, CPA1, CLDN1 (key SNPs), PRSS1, PRSS2, PRSS3, PRSS1-2 locus, GGT1 and UBR1)), lipid metabolism (APOA5, APOC2, FABP, LPL), inflammation (IL10, IL22, IL22RA1, IL22RA2, IL23R) and drug metabolism (COMT, HTR2A, CYP2C19, CYP2D6, CYP3A4, CYP3A5, OPRD1 and OPRM1) in children with CP/ARP who undergo WebMAP vs WebED. Risk stratification analysis will be done to identify genotypic factors that will predict response to treatment.

Hypothesis 3: Baseline clinical characteristics (i.e. demographics, age at diagnosis, abdominal pain frequency and severity, number of pancreatitis attacks, imaging findings), and baseline emotional and family functioning will predict pain and health outcomes at 6 months.

2. Background

2.1. Relevant prior experience and gaps in current knowledge:

Current state of the science: pediatric pain self-management interventions. Psychological treatments for pediatric chronic pain have included predominantly cognitive-behavioral therapy (CBT) self-management interventions such as pain education, relaxation training, cognitive skills, behavioral activation, and relapse prevention. Psychological therapies are effective in reducing pain intensity and pain-related disability of children and adolescents with chronic pain, including abdominal pain 15. To date, there are no established pediatric pain self-management interventions for pediatric CP/ARP.

Challenges to provide pain self-management interventions. Despite the effectiveness of pain self-management programs, many barriers prevent children from receiving self-management for chronic pain: i) children/caregivers may be reluctant to seek out mental health services for pain management, ii) access may be limited due to geographic restrictions (e.g., available only in tertiary centers), iii) small number of trained clinicians are available to deliver the therapies, iv) families often experience burden in taking time off school and work, and v) direct and indirect costs of therapy visits are often prohibitive. Highly trained personnel deliver

these therapies in individual or group sessions in specialty clinics; therefore, services are not widely available for community and home-based settings. These barriers have led our group to develop a highly successful and well-accepted childhood pain self-management intervention delivered via Internet.

Rationale for web and mobile technologies to enhance delivery of pain self-management care for pediatric CP/ARP. We took advantage of information and communication technology to expand opportunities for intervening with families remotely, thus greatly extending the reach of clinical services for pain self-management. There is now strong evidence for internet-delivered chronic pain self-management interventions in both adult and pediatric populations 16 with improvement in pain and disability. In addition to improving access, these technologies empower youth to take an active role in managing their condition by providing “in the moment” access to pain coping strategies.

2.2. Relevant preliminary data:¹

Evaluation of Web-Based Management of Adolescent Pain (WebMAP). [name] developed an Internet delivered CBT pain intervention called WebMAP that includes 8-10 weeks of online modules to teach relaxation skills, pain coping strategies, and parent behavioral and communication techniques to youth with mixed chronic pain conditions. In the initial RCT with 48 youth (11–17 years) with a variety of pain conditions (e.g., headache, stomachache, musculoskeletal pain), significant reductions in pain and disability were found for youth receiving WebMAP compared to a wait-list control group.⁵¹ Following up on this initial trial, [name] recently completed a second large multicenter RCT of WebMAP involving 273 adolescents (ages 11-17 years) with chronic pain and their parents from 14 centers in the U.S. and Canada 23. Adjunctive to treatment in pain clinic, youth were randomized to one of two Internet treatments, WebMAP (adolescent and parent CBT pain intervention, n=138) vs WebED (education control, n=135). Close tracking and monitoring procedures led to an excellent retention rate in the trial (94.2% post-treatment, 92.4% at 6-months, and 92.4% at 12-months), and superb compliance (> 80%) with both treatment conditions (education and CBT). In support of our primary hypotheses, youth receiving Internet CBT achieved greater improvement in pain-related disability compared to the Internet Education group from baseline to 6-month follow-up ($b = -1.13$, $p = 0.03$, $d = -0.25$). There were small effects of Internet CBT on improving depression in the Internet CBT group (relative to Internet Education) from baseline to post-treatment ($b = -0.59$, $p = 0.04$, $d = -0.09$). Similarly, adolescents receiving Internet CBT showed a significant reduction in pain-related anxiety relative to the Internet Education group from baseline to post-treatment ($b = -1.33$, $p = 0.04$, $d = -0.13$). As hypothesized, there were significant, small to medium effects of treatment on reducing maladaptive parent behaviors. Parents in the Internet CBT group demonstrated a significantly greater reduction in protective behaviors compared to the Internet Education group from baseline to post-treatment ($b = -0.26$, $p < 0.001$, $d = -0.49$) and from baseline to six-month follow-up ($b = -0.19$, $p = 0.001$, $d = -0.40$). Effects were maintained through the 12-month follow-up 26. WebMAP has been adapted and tested in several other pediatric painful disorders including a completed trial in chronic headache 25, sickle cell disease (Palermo, et al, in press) and an ongoing trial with 300 youth with functional abdominal pain (NIH R01HD076983, PI: [name]). Our data and experience so far confirm WebMAP as an efficient, easily accessible tool with great potential to reduce pain-related disability and parental maladaptive behaviors that perpetuate and sustain painful disorders.

Pilot WebMAP study in children with ARP and CP. For this application, we collected preliminary data from WebMAP delivered to 2 youth with ARP and 4 youth with CP to assess feasibility and interest in learning cognitive-behavioral pain management skills. Youth were ages 11-16 years and recruited from Seattle Children's Hospital and University of Pittsburgh (2 of the 21 sites proposed in this application). Treatment engagement was good; youth logged into WebMAP an average of 8 times (range 2 - 21) and parents logged in an average of 10 times (range = 2 - 18) over the 8-10 week treatment period. Youth and parents completed a mean of 5.2 treatment modules (4 of 6 families completed the full program). On the Treatment Evaluation

Inventory, children's ratings indicated moderate acceptability ($M = 28.2$, scores > 27 indicate moderate acceptability). Similarly, parents rated moderate acceptability ($M = 31.3$). To understand participants' experience with WebMAP, we conducted qualitative interviews with 3 parent-child dyads. Overall, participants reported that the CBT program was a helpful tool for coping with pain. We learned that some children with ARP and their parents were less likely to complete the WebMAP program due to lack of experienced pain during the course of the intervention, which reduced the relevance of the treatment program. Because WebMAP is designed for treatment of chronic pain, this pilot work informed our decision to focus the proposed trial on youth with CP/ARP with pain frequency once per month or greater. Our preliminary data support that web-based self-management of pain is acceptable to children with CP/ARP and their parents.

2.3. Scientific or scholarly background:

Chronic pancreatitis causes significant burden in the pediatric population. Recent studies estimate an increase in the incidence of childhood acute pancreatitis (AP) at 3.6-16.1 cases per 100,000 children per year^{1, 2}, which is similar to the incidences reported in adults³. Most children with pancreatitis have a single acute episode that resolves without complications. However, 15-35% of children with AP develop acute recurrent pancreatitis (ARP) and some progress to chronic pancreatitis (CP, incidence ~ 0.5 -2.73 per 100,000 per year)⁴⁻⁷. Many children with CP/ARP are admitted to the hospital for recurrent attacks of AP⁷. In the INSPPIRE cohort, children with CP/ARP have high disease burden, including abdominal pain, frequent emergency room visits, missed school days and recurrent hospitalizations^{8, 9}. The estimated average annual cost of pediatric CP/ARP is \$40,589 per child in the INSPPIRE cohort¹⁰. By extrapolating these costs, pediatric CP/ARP may result in \sim \$64 million to the US healthcare system per year. Although relatively uncommon, pediatric CP/ARP is associated with high disease burden and healthcare costs.

The etiology of CP is complex. CP is a syndrome of progressive inflammation, remodeling, fibrosis and failure of the exocrine and endocrine pancreas over time. There are multiple etiologies linked to environmental and genetic factors, with genetics being a major factor in at least 75% of children^{8, 9}. Genetic factors define multiple pathogenic pathways, as well as disease modifiers and risk of complications, including fibrosis, diabetes, exocrine pancreatic insufficiency and pain¹¹. Thus, assessing genetic and environmental risk and mechanisms as cofactors in complex disease models is critical.

Pain is associated with high disease burden and economic costs in pediatric CP/ARP. Eighty-one percent of children report abdominal pain ($\sim 43\%$ some form of constant pain) and pain is the major driver of cost in the INSPPIRE population¹⁰. Children with constant pain experience more emergency room visits, miss more school, and require more hospitalizations compared to those without chronic pain^{8, 10}. Forty-one percent of children with CP in our cohort use an opioid to control pain. Despite the frequency of pain and its relevance to high socioeconomic burden, there are no non-pharmacologic pain interventions available for children with CP/ARP. As the disease progresses and pancreatic tissue is replaced with fibrosis, intrapancreatic nerves undergo neuropathic changes and become "sensitized" to transmit stimuli even after the painful stimulus is removed¹². This "central sensitization" is the main reason why pain persists even after the pancreas is resected^{13, 14}, rendering therapies such as total pancreatectomy and islet autotransplantation (TPIAT) ineffective for pain control for many patients. Children with chronic pancreatitis urgently need effective, early therapies delivered in childhood to reduce pain, pain-related disability and exposure to narcotics. Large and well-established cohorts, such as INSPPIRE allow us to test the effectiveness of non-pharmacological pain interventions in children with CP/ARP.

Impact of proposed project on improving scientific knowledge and clinical care. To maximize efficiency, this chronic pain self-management program is geared to the unique developmental and informational needs of youth with CP/ARP. The intervention is expected to enhance awareness and empower self-management early in the disease course. Given that the burden of pain worsens with age,

early intervention is critically important for interrupting negative cycles of pain and associated functional impairments. This will be the first project to test the efficacy of an early, non-pharmacological pain intervention in children with CP/ARP and potentially to identify modifiers of treatment effects.

2.4. Prior approvals:

We conducted a pilot study IRB # STUDY00000137.

3. Study Endpoints²**3.1. Primary and secondary endpoints:****3.2. Primary or secondary safety endpoints:**

For section 3.1: Primary endpoint is greater reductions in pain-related disability. Secondary endpoint is the reduction of pain, anxiety/depressive symptoms, opioid use, and HRQOL.

For section 3.2: There are no safety endpoints in this study.

4. Drugs, Devices and Biologics³**4.1. Manufacturer and name of all drugs, devices and biologics:**

N/A

4.2. Description and purpose of all drugs, devices and biologics:

N/A

4.3. Regulatory status of all drugs, devices and biologics:⁴

N/A

4.3.1. Drugs or Biologics:

☐ IND Exempt. Explain:⁵ [Click here to enter text.](#)

☐ IND.

4.3.2. Devices:

☐ IDE Exempt. Explain:⁶ [Click here to enter text.](#)

☐ Abbreviated IDE / Non-Significant Risk. Explain:⁷ [Click here to enter text.](#)

☐ IDE / Significant Risk.

4.4. Plans to store, handle, and administer any study drugs, devices and biologics so they will be used only on subjects and be used only by authorized investigators:

N/A

5. Procedures Involved**5.1. Study design:⁸**

A randomized controlled double-blinded trial will be conducted. Families will be randomized to either WebMAP or WebED (education control). 260 children (ages 10-19 years) with CP/ARP and their parents/caregivers (if possible) will be recruited from the INSPPIRE network and pancreatitis-related community organizations such as the National Pancreas Foundation (NPF) and Mission Cure. The intervention phase will last 8-12 weeks. Assessments will occur at baseline (T1), immediately after intervention (2 months; T2), and repeated at 6 months postintervention (T3) to assess maintenance of treatment gains. Primary outcome is pain-related disability (T2, T3).

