5.2. Research procedures:⁹

Recruitment Study Procedure. 1) referral to the Web-MAP CP study by a collaborating INSPPIRE center or completion of community interest form, 2) telephone intake interview to determine study eligibility and explain study procedures, 3) coordinator will conduct informed consent over the phone and via secure REDCap link,

Study Procedure. 1) complete T1 (Baseline) study assessment via REDCap, 2) randomization to WebMAP or WebED program 3) phone instructional session for logging into the website and using the program. 4) participation in the randomized condition (see information table on each program), 5) complete T2 (about 2 months after baseline) via REDCap and 6) completing T3 6-month follow-up evaluation via REDCap.

Randomization Procedures. Using block randomization, children and parents will be randomized to two groups: WebMAP or WebED. Both groups will continue to receive standard medical care from a specialized pediatric pain clinic. We will generate a random numbers table using an online calculator to derive a randomization assignment in blocks of 4 for ID numbers.

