WebMAP Group: The Web-MAP program teaches relaxation skills, pain coping strategies and parent behavioral and communication techniques to youth with chronic pain. Child participants will practice 8 skills. The skills included in Web-MAP are: 1) education about chronic pain and pain management, 2) recognizing stress and negative emotions, 3) relaxation and deep breathing, 4) implement coping skills at school, 5) cognitive skills, 6) lifestyle interventions, 7) staying active, and 8) relapse prevention. Parents will practice skills including: 1) education about chronic pain, 2) recognizing stress and negative emotions, 3) operant strategies I – attention and praise for positive coping, 4) operant strategies II –rewards for positive coping and reaching school goals, 5) modeling, 6) lifestyle, 7) communication, and 8) relapse prevention. Participants can also track daily activities and skills they used on the computer. Participants randomized to the WebMAP program will be practicing one of the 8 skills each week and will be contacted if they have not completed that skill after a week has passed. Mixed methods (email/text/phone calls if given permission by participant) will be used to contact participants to give reminders to continue logging into the program. Participants will receive their usual care and Web-MAP will not take the place of any aspect of their standard treatment

WebED Group. The purpose of the patient education control group is to control for time, attention, and computer usage. This group will serve as an attention control condition. Children will continue with the standard medical care that has been prescribed for their pain problem. Children and parents will be provided with access to a revised version of the Web-MAP study website, which will have two functional components: 1) information from publicly available educational websites about pediatric chronic pain management, 2) diary and assessments. This version of the website differs from the one accessed by the treatment condition in that it does not provide access to behavioral and cognitive skills training via treatment modules for children and parents.

During participation, a member of the study team would call/email/text to check in and to see if there are any problems or questions about using the program.

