5.3. Data sources that will be used to collect data about subjects:¹⁰

Measures	Description	T1	T2	T3	Rater
Family Information Form	Parents report on demographic and socioeconomic information, and adolescent health history.	X			Parent
Pediatric Pancreatitis Questionnaire	Parents report on acute/chronic pancreatitis clinical history and diagnosis.	X			Parent
Pain Intensity, frequency, and duration	Pain intensity will be rated on the online diary using an 11-point NRS. Pain frequency and duration are averaged over each seven-day measurement period.	X	X	X	Child
Child Activity Limitation Interview (CALI-9)	Daily diary version of the CALI-9 will be used to rate perceived difficulty in completing 9 daily activities as a measure of pain-related disability.	X	X	X	Child
PROMIS Pediatric Emotional Distress Scales	8-item scale of anxiety that assesses fear (e.g., fearfulness), anxious misery (e.g., worry) and hyperarousal (e.g., nervousness) and 8-item scale of depressive symptoms.	X	X	X	Child
Pain Self-Efficacy	The Pain Self-Efficacy Scale is a 7-item measure that assesses the child's beliefs in carrying out activities when in pain. The scale has demonstrated good internal consistency, cross-informant reliability with parent report, and strong construct validity.	X	X	X	Child
PROMIS Pain interference	Pediatric Short Form assesses pain-related interference	X	X	X	Child
Bath Adolescent Pain Questionnaire–Parent Impact	Assesses changes in perception of burden, family functioning, and emotional distress associated with parenting youth with chronic pain.	X	X	X	Parent
Health-related quality of life	Pediatric Quality of Life Inventory will assess broad impact of health on child and family	X	X	X	Parent, Child
Health services utilization	Client Services Receipt Inventory for Pain assesses inpatient and outpatient visits, medications, other treatments, and indirect costs as reported by the parent	X		X	Parent
Treatment satisfaction and engagement	Treatment satisfaction (10 item measure with Likert ratings and open-ended items about content and delivery method) (P, A); Web usage		X		n/a

	(logins, completion of assignments, etc.) collected from the administrative website				
Adverse events	Adverse event form will be used.		X	X	Parent, Child
Abdominal Pain Index	Assesses child abdominal pain frequency, duration, and intensity.	X	X	X	Parent, Child

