12.1. Reasonably foreseeable risks to subjects (include each study population, each arm, and optional procedures):

This study is minimal risk. There are potential risks around emotional distress, time commitment, and confidentiality. Although asking about physical symptoms and mood/behavior does not typically result in any distress, there is a small risk of emotional distress. There is a potential risk of loss of confidentiality.

12.2. Procedures with unforeseeable risks:

N/A

12.3. Procedures with risks to an embryo or fetus should the subject be or become pregnant:

N/A

12.4. Risks to others who are not subjects:

N/A

12.5. Procedures performed to lessen the probability or magnitude of risks:

Participants will be advised they can skip any questions they feel uncomfortable answering. To support confidentiality, adolescents will be asked to complete questionnaires independently. We will make every effort to protect this data. For example, all data will be coded with a unique ID number. Participants will be informed of their right to refuse to participate in any part of the data collection and given the phone numbers of the PI and the Seattle Children's IRB in the event that they desire further information or would like to issue a formal complaint.

13. Potential Benefits to Subjects

13.1. Potential benefits that individual subjects may experience from taking part in the research.³¹

Participation in this research study may or may not benefit the subject. The 8-week Web-MAP program may help to increase daily functioning and decrease pain intensity in children and teens who complete this program as it has shown effectiveness in other youth with chronic pain.

14. Data Analysis/Management

14.1. Data analysis plan, including statistical procedures:

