20.10. Waiver or Alteration of Consent Process

20.10.1. Reasons for requesting a waiver or alteration of informed consent:⁵⁷

We are requesting a waiver of consent for children who turn 18 whose private identifiable information is still being used for data analysis purposes, but are no longer actively participating in the study. The justifications for this waiver are here:

20.10.2. Consent Waiver/Alteration Criteria justifications:⁵⁸**20.10.2.1.** The research involves no more than minimal risk to the subjects because:

Participants are only asked to complete online surveys and log in to a website that would provide either education about chronic pain or skills training to manage chronic pain. There are no significant risks involved in participation. Furthermore, data analysis involves no additional risk to participants whatsoever, as participants do not complete any activities and are no longer involved.

20.10.2.2. The waiver or alteration will not adversely affect the rights or welfare of the subjects because:⁵⁹

The waiver of consent would not adversely affect the rights or welfare of subjects because any publication of research results would never reveal an individual's identity either directly or indirectly. Furthermore, all survey responses will be linked with a unique study ID to protect participant confidentiality, and all study documents/information will be stored in secure, password/firewall-protected servers and databases.

20.10.2.3. The research could not practicably be carried out without the waiver or alteration because:⁶⁰

Due to the age range of the study, most participants would turn 18 before data collection & analysis is complete, so the research could not be practicably carried out if the study team had to contact all of them again and re-consent. Additionally, study staff will not be in contact with participants after their study participation is complete, and it would be impracticable to conduct the research if the study team had to reach participants for the purposes of obtaining consent due to significant time lapse between participant completion, turning 18, and data collection/analysis, along with changing contact information or life circumstances. In addition, not including data from the entire participant population would bias study results.

20.10.2.4. Whenever appropriate, the subjects will be provided with additional pertinent information after participation:

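### The plan calls the trial double-blinded and placebo controlled, but names no masked party, describes no masking, and takes its primary outcome from the child's own report

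*Combined protocol and SAP*

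**What the plan says.** **The label.** Section 1.1 says: "This project will deliver a first ever randomized, double-blinded and placebo controlled nonpharmacological pain intervention to children with CP/ARP". Section 1.2 (Hypothesis 1) again calls the trial double-blinded, and section 5.1 says: "A randomized controlled double-blinded trial will be conducted".

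**The arms.** Section 5.2 gives WebMAP families eight child skills and eight parent skills, practised one per week. WebED families use a revised version of the same website, with public educational material plus diary and assessments. Section 5.2 calls this an attention control, meant to control for time, attention and computer usage, and says "it does not provide access to behavioral and cognitive skills training via treatment modules for children and parents".

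**Contact after randomization.** Section 5.2 lists a "phone instructional session for logging into the website and using the program". WebMAP families are also contacted when a week passes with a skill unfinished. A general check-in by the study team is printed after the WebED description and may apply to both arms.

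**The outcome.** Section 5.3 says: "Daily diary version of the CALI-9 will be used to rate perceived difficulty in completing 9 daily activities". The rater is the child, at T1, T2 and T3. Section 5.1 names T2 and T3 as the primary timepoints.

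**The concern.** Double-blinded and placebo controlled are claims about which biases a design excludes. They need a masked party and a means of masking, and the plan supplies neither. What it does describe (programmes with different content, contact triggered by progress in one arm, a self-rated primary outcome) is the setting in which expectation and the wish to report improvement can differ between arms.

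At stake is what the trial can conclude. If the label is carried into the report, readers will treat expectation effects as excluded, although the plan has no procedure to exclude them and no measurement to gauge them. Expectancy and perceived allocation cannot be recovered if they are not asked at the time.

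**Working it through.** **1. Label against procedures.**

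| Element | What the documents show | Consequence |
|---|---|---|
| Masked party | None named in 1.1, 1.2, 5.1, 5.2 or 14.1 | The label has no content that can be checked |
| Allocation list | 5.2: blocks of 4 from an online calculator; no holder named | Staff masking cannot be inferred from it |
| Comparator | 5.2: attention control, no skills modules | Education control, not a matched placebo |
| Support staff | 5.2: WebMAP contact triggered by an unfinished skill | Whoever makes that contact knows the arm |
| Families | 5.2: they use the programme they were given | They see its content; whether they know which programme is under test is not stated |
| Primary rater | 5.3: child | Masking staff cannot by itself protect the outcome |
| Check on masking | 5.3: no expectancy or perceived-allocation item | Any influence of expectation cannot be assessed |
| Analyst | 14.1: no coded-arm step | Not described as masked |

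**2. The plan's own sample size (section 10.4).** Inputs: SD 4, difference 1.5, significance level 0.05 (taken as two-sided), power 80%.

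n per arm = 2 × (1.960 + 0.842)² × 4² / 1.5² = 111.6, rounded up to 112. This matches the plan. Power at 112 is 80.1% by the normal approximation and 79.8% by the t-test. A one-sided test would need 88, so the plan's figure is two-sided.

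**3. Sensitivity to a reporting shift (illustration only).** Assume no true effect, and a shift of b points in favour of WebMAP arising from expectation rather than skills. The documents give no value for b.

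SE of the difference = 4 × √(2/112) = 0.5345.

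Rejection rate = Φ(b/SE − 1.96) + Φ(−b/SE − 1.96).

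| Assumed shift b | b/SE | Two-sided rejection rate |
|---|---|---|
| 0 | 0 | 5.0% |
| 0.25 | 0.47 | 7.5% |
| 0.5 | 0.94 | 15.5% |
| 0.75 | 1.40 | 28.9% |
| 1.0 | 1.87 | 46.5% |

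The noncentral t with 222 degrees of freedom gives 15.4% at 0.5 and 46.1% at 1.0, so about 15% and 46% either way.

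**4. Scale.** The planned difference is 1.5 points, so shifts of 0.5 and 1.0 are 33% and 67% of it. The earlier multicentre WebMAP trial in section 2.2 reports a whole effect on disability of 1.13 points; a shift of 1.0 would be 1.0/1.13 = 88% of that.

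**The case against.** A reader might infer more than this: that WebED children know they are the controls, and that the trial has no blind at all. The documents do not support that. They show that families see their own programme's content, not that they are told, or can tell, which programme is being tested. WebED runs on a revised version of the same site and is built to match time, attention and computer use, so some families may not know the hypothesis.

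Two passages tempt one to the stronger reading. Section 13.1 attaches the possible benefit to one arm: "The 8-week Web-MAP program may help to increase daily functioning and decrease pain intensity in children and teens who complete this program". Section 20.10.2.1 says participants "log in to a website that would provide either education about chronic pain or skills training to manage chronic pain". Both are protocol answers to ethics-board headings. They do not show what families read; the consent forms, letters and flyers are not available here, and no fault in them should be presumed.

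Three further points have force:

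- Support staff do not rate the outcome. Section 24.1 has families complete assessments at home through REDCap/WebMAP, so staff knowledge can act only indirectly, through contact.
- The 1.0-point case may be extreme. In the earlier trial against the same type of control, the post-treatment effects on depression and pain-related anxiety were d = −0.09 and −0.13, or 0.36 and 0.52 points at SD 4. This is only suggestive, because protective parent behaviour in that trial moved by d = −0.49.
- Participant masking is hard to achieve when a skills programme is compared with education, and correcting the label changes no endpoint, model or sample size.

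These points limit what can be said about families and about the size of any bias. They do not rescue the label. Unawareness of the hypothesis, if intended, has to be written down; and with support staff who know the arm and no other masked party named, the description is not double-blinded.

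**Conclusion.** The point holds as a mismatch between the design label and the described design. Three sections claim double blinding and one claims a placebo; no masked party or masking procedure is documented, the comparator is an education control, at least the WebMAP support staff know the arm, and the primary outcome is child-reported. A between-arm difference cannot be presented as protected by double blinding.

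The textual finding rests on no assumption about numbers. The size of any resulting bias is unknown. The rise from 5% to about 15% or 46% depends on an assumed shift of 0.5 or 1.0 point, no true effect, and the planning values of SD 4 and 112 per arm; it shows sensitivity and is not an estimate. Whether families are masked to the hypothesis stays open.

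**What to change.** 1. In section 1.1, replace placebo controlled with attention (education) controlled. In 1.1, 1.2 and 5.1, replace double-blinded with a statement of who is masked and to what: support staff not masked; families see their programme's content and are at most masked to the hypothesis, if the family-facing materials keep it so; outcomes self-reported. Carry the same statement into the trial's conclusions.
2. In section 14.1, give the analyst arms coded A and B until the primary model is final.
3. In section 5.3, add short REDCap items for child and parent: expected benefit after the phone instructional session, and perceived allocation once the T3 outcome measures are complete. The allocation question should not be asked at T2, because T3 is also a primary timepoint and the question could prompt guessing. Report both by arm beside the primary result, noting that late guesses can reflect benefit received.

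Cost: a less favourable design label, a few extra questionnaire items, a coded dataset and an IRB amendment. The sample size stays at 112 evaluable and 130 enrolled per group.
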